## **5. Specific Aims:**

The specific aims for this project are:

Aim 1: To determine the relationships between blunted airway somatosensation, reflex cough sensitivity and effectiveness, and swallowing function in people with PD.

Hypothesis 1: We predict that blunted airway somatosensation will appear earlier (years 0 – 5 post-diagnosis) in the disease process than either cough or swallowing dysfunction, and that by 6-10 years post-diagnosis, blunted respiratory somatosensation will correlate with reduced reflexive cough sensitivity and effectiveness, and decline in swallow function and safety.

Specific aim 2: To determine whether measures of discriminative and affective processing of general airway sensation is/are associated with deficits in reflex cough and swallowing function in people with PD.

Hypothesis 2: People with PD will exhibit reduced discriminative processing components of airway stimuli. With disease progression, measures of affective processing components will decline and this will directly correlate with diminished reflex cough sensitivity and swallowing function.

Specific aim 3: To determine whether over-filtering of airway stimuli is associated with swallowing or cough deficits in people with PD.

Hypothesis 3: Over-filtering of airway stimuli will be associated with deficits in reflex cough and swallowing function in people with PD.

Aim 4: Determine the relationships between observable motor aspects of swallowing, cough, and cough sensitivity over a 3-year time period in people with PD.

Hypothesis 4: Swallowing safety and physiology in people with PD will exhibit significant differences over 3 time points, spaced 10 – 18 months apart. For people within 9 years of PD diagnosis, reduced reflex cough sensitivity will not be a sensitive and/or specific indicator of swallowing dysfunction. However, for those with a greater disease duration (10+ years), reflex cough sensitivity will be a sensitive and specific biomarker of swallowing dysfunction.

## 6. Research Plan:

### **Protocol 1 (Aims 1-3)**

This prospective experimental study will include male and female adults with PD, as well as a control group consisting of healthy adults. We aim to recruit 30 participants in each group. We will recruit PD participants from the patient population at UF Fixel Institute for Neurological Diseases. Healthy control participants will be recruited from the community population, including spouses and caregivers of PD participants, as well as HealthStreet. All participants will provide written consent before enrollment into the study, which will be approved by Institutional Review Board (IRB) at the University of Florida.

#### ***Inclusion criteria:***

- 1.) Between the ages of 45 and 85 years
- 2.) Diagnosis of PD, Hoehn and Yahr stages I – IV, by a fellowship trained neurologist arriving at the diagnosis of PD by applying strict UK brain bank criteria (PD participants only)

#### ***Exclusion criteria:***

1. Neurological disorders other than PD (i.e., stroke, multiple sclerosis, etc.)
2. Difficulty complying due to neuropsychological dysfunction (i.e., severe depression)
3. Allergy to capsaicin or hot peppers
4. History of cancer in the head, neck, or lungs (not including skin cancer on the head/neck that did not require major surgical resection significantly altering anatomy or radiation to head/neck tissue).
5. History of smoking in the past 5 years
6. Any neurological disorder including PD (Healthy control group only)

*Experimental design and procedures:* This prospective experimental study will be completed in one or two study visit(s) taking between 1 and 3 hours each. Testing will be conducted in a quiet clinical research space. Verbal and written informed consent will be obtained by qualified members of the investigative team. Following informed consent, all participants will complete a health history questionnaire to assess inclusion/exclusion criteria (Appendix 1). As well, the consenting investigator will review the electronic medical record to ensure inclusion/exclusion criteria are met.

The experimental protocol will consist of 1.) Review of electronic medical record to determine participant disease status 2.) Baseline pulmonary function measures 3.) Baseline depression and apathy scales, 4.) Inspiratory resistive load presentation 5.) Reflex cough assessment 6.) fluoroscopic swallow study 7.) Measures of event-related sensory evoked potential (SEP) to an airway stimulus.

#### ***Participant disease status:***

A qualified member of the investigative team will review the electronic medical record and record the following information for each PD participant: disease severity (Unified Parkinson's Disease Rating Scale, Hoehn & Yahr score), medications, levodopa equivalent dose, and surgical status (specifically presence, target site, and laterality of deep brain stimulator(s)).

***Baseline pulmonary function measures:***

We will analyze pulmonary function in all participants. The forced expired volume in the first second (FEV1) of a forced vital capacity (FVC) maneuver will be measured for each participant using a digital spirometer (Spirovision 3+m, Futuremed; or Koko spirometry, inspire health). Maximum inspiratory and expiratory pressure (PiMax; PEMax) will be measured with a manometer (MicroRPM, Micromedical Inc.). We will use standard procedures, as put forth by the American Thoracic Society, for measuring FVC, FEV1, the ratio of FEV1/FVC, and PiMax/PEMax.

***Baseline depression and apathy:***

Participants will complete 2 validated scales, the Beck Depression Index-II (BDI-II) and Starkstein Apathy Scale (AS) to determine baseline depression and apathy scores.

***Inspiratory resistive load presentation:***

Participants will rate perceived difficulty of breathing in response to various resistive loads applied to single inspirations during tidal breathing in order to assess general respiratory somatosensation. The participant will be seated in a chair, separated from the investigator and experimental apparatus. The participant will be instructed to “relax and breathe” through a facemask connected to a non-rebreathing valve (Hans Rudolph, 2700 series) in line with a differential pressure transducer. The inspiratory port of the valve will be connected to the resistive loading manifold. The manifold consists of 5 differential resistors ranging from 2.5 – 40 cmH2O/lps of resistive pressure, separated by stoppered ports, as well as a no load condition. The load is applied by removing the stop for an entire inspiratory breath, and then replacing the port to continue resting tidal breathing. The pressure transducer will provide measures of mouth pressure and airflow, which will be digitized (PowerLab, ADInstruments) and recorded to a desk top computer using LabChart software (ADInstruments). Following each loaded breath, the participant will provide an estimate of the perceived difficulty of breathing using a modified Borg scale.

Participants will be familiarized with the loads in a practice session prior to initiating the experimental protocol. The resistive loads will be applied in a randomized block design, with each loaded breath separated by at least three unloaded breaths. Two blocks will be completed with each load presented between 3 and 5 times within each block. Therefore, there will be a total of between 15 and 25 loaded breaths (3-5 loads x 5 presentations) per block. Following the loaded breath, and one random non-loaded control breath, the participant will be asked to estimate the perceived difficulty of breathing on the Borg scale.

***Reflex Cough Assessment Procedures:***

Participants will be outfitted with a facemask covering the nose and mouth. The facemask will be coupled to a pneumotachograph, differential pressure transducer, and have a side port with a one-way inspiratory valve for nebulizer connection. The nebulizer will be connected to a dosimeter that delivers aerosolized solution during inspiration with a delivery duration of 2 seconds. The cough airflow signal will be digitized (Power Lab Data Acquisition System) and recorded (LabChart 7; ADInstruments, Inc.) to a laptop computer.

Participants will be seated for an initial 30 seconds of quiet breathing in order to acclimate to the facemask. Participants will then complete a capsaicin challenge with three randomized blocks of

0, 50, 100, 200, and 500  $\mu$ M capsaicin dissolved in a vehicle solution. Participants will be given the instruction “cough if you need to” prior to capsaicin delivery. The solution will be administered automatically upon detection of an inspired breath and there will be a minimum of one minute between each trial. Participants will be provided water to drink between trials. Following each capsaicin trial, participants will rate their urge-to-cough on a modified Borg Rating Scale measured 0-10, where 0 is no urge, and 10 is maximal urge. Our research group has extensive experience utilizing this methodology to induce cough (e.g., (1, 34-36)). We also hold an FDA IND # 76866 for the use of capsaicin in the study of cough reflex sensitivity and motor pattern.

***Voluntary cough procedure:***

Voluntary cough will be assessed using the same equipment used for reflex cough testing, without the nebulizer attached to the side port (side port is capped off). The participant will be asked to produce a sequential voluntary cough three times into the facemask attached to the pneumotachograph, and to maintain a comfortable seated position for all cough testing. Each cough trial will be separated by approximately 1 minute of quiet breathing. Participants will be given the following instructions for cough production: “When you are ready, cough as if something has gone down the wrong pipe.”

**Cough outcome variable:** The concentration of capsaicin that elicits the 2-cough response (C2) will be recorded and serve as our measure of cough reflex sensitivity. Additionally, airflow measurements will be derived from the reflex and voluntary cough waveforms. Measurements will include compression phase duration (CPD), peak expiratory flow rate (PEFR), and peak expiratory flow rise time (PEFRT) and cough volume acceleration (CVA=PEFR / PEFRT).

**Urge-to-cough (UtC):** Following each capsaicin trial participants will rate their urge-to-cough (UtC) on a modified Borg rating scale, where 0 is no UtC, and 10 is maximal UtC. The UtC provides information regarding participants’ perceived magnitude of the stimulus.

***Fluoroscopic swallow study:***

Swallowing function and physiology will be assessed using high-resolution digital fluoroscopy at a pulse rate of 30 frames per second, digitally stored for retrieval and offline analysis. Participants will be seated in the lateral viewing plane. Three trials each of the following swallowing tasks will be performed: Thin hold of 10 – 20mL liquid barium administered via cup, 5-10mL of pudding-thick barium administered via spoon, and 3-oz thin liquid sequential swallow administered by cup. Should aspiration be observed on the thin liquid swallows, we will omit the third trial and administer the pudding. Should aspiration occur with the pudding bolus, we will omit the remaining boluses (bail-out criteria). This protocol was selected because it mirrors our clinical protocol, and thus it would be possible to reduce participant burden and radiation exposure by replacing a clinical study with a research study, or vice-versa.

Our primary swallowing outcome measure will be score on the penetration-aspiration scale (PAS) measured from the videofluoroscopic evaluations of swallowing. Our secondary swallowing outcome measures will provide metrics of swallow physiology including swallow reaction time (SRT; H1 to B1), duration of laryngeal vestibule closure (dLVC; LVC to LVO),

duration to laryngeal vestibule closure (LVC) from hyoid burst (H1) (dtLVC\_H1), duration to LVC from bolus head in pharynx (B1) (dtLVC\_B1) and pharyngeal transit time (PTT; B1 to B2).

***SEP Procedures:***

Participants will be asked to refrain from strenuous physical activity, large meals and caffeine for at least four hours prior to participating. The participant will be seated in a private, sound/electrical shielded experimental room, with his or her back, neck and head comfortably supported. The participant will be monitored with a video camera. The electroencephalogram (EEG) will be collected using a 64-channel Electrical Geodesics Inc. (EGI; Eugene, Oregon, USA) net and amplifier system (amplification 20 K, nominal bandpass 0.10–100 Hz). Netstation software will be used for continuous recording of EEG data.

The 64-channel EGI electrode net will be placed on the head of the participant. Each participant will be instructed to breathe normally through a mouthpiece connected to a non-rebreathing valve. The inspiratory port will be connected to an airflow sensing pneumotachograph and inspiratory occlusion valve that obstructs the inspiratory airflow. Airflow, mouth and occlusion valve pressures will be sensed with differential pressure transducers and signal conditioners. Paired, identical inspiratory occlusions will be presented by silently inflating the occlusion valve approximately 50ms after the onset of inspiration, and will last for 150 ms. Each occlusion pair will be separated by a 500 ms interstimulus interval. The occluded breaths will be separated by at least 2 unoccluded breaths. The total time required for the presentation of the occlusions will be 700ms after the onset of inspiration, which is within the normal 1.5 second inspiratory duration. Up to 100 occlusion pairs will be delivered in each experimental trial. The latency from stimulus delivery and amplitude for the P1, N1, P2 and N2 peaks will be recorded from both the first (S1) and second (S2) occlusion.

***Attend/ignore conditions:*** In order to understand and account for the effect of attention to the stimulus on the latency, amplitude, and gating of the airway SEP peaks, we will perform the SEP procedure under 2 conditions: attend and ignore. For the attend condition, participants will be instructed to pay attention to their breathing and press a button one time whenever they feel an obstructed breath. In the ignore trial, the subject will not be given any instructions to pay attention to their breathing, and will be asked to watch a series of neutral affective pictures (IAPS; (58)) and ignore their breathing.

***SEP outcome measures:*** *a. SEP peaks:* The latency and amplitude of the SEP P1 and N2 peaks under the attend and ignore conditions are the primary outcome variables. Secondary outcome measures include the latency and amplitude of the other component peaks, including N1 and P2 peaks. *b. SEP Gating:* The ratio of the amplitude the peaks generated by the first and second paired occlusions will be calculated for each peak, within the attend and ignore conditions. The primary outcome variable will be the ratio of S2/S1 for the P1 and N2 peaks, and the S2/S1 ratio for N1 and P2 peaks will serve as secondary outcome variables.

## **Statistical Analysis**

**Aim 1:** A multiple regression analysis will be conducted with the slope magnitude estimation as the outcome and disease duration, age, and sex as the independent variables in addition to their mutual interaction terms. Model selection technique will be adopted to select the optimal parsimonial model deemed for the data. We will also perform subgroup analysis to

compare the slope magnitude estimation between PD patients with PAS (penetration-aspiration scale) no more than 2 and PD patients with PAS greater than 2 by adjusting confounding factors of age, gender and BMI, etc. to demonstrate that reduced slope of magnitude estimation is present in PD patients regardless of PAS status. We will include other swallow and cough outcome variables in this model to determine relationships between dependent variables.

**Aims 2 and 3:** We will first fit a multiple regression model with P1 and N2 peak amplitude and gating ratios as the dependent variable and condition (1 = attend and 2 = ignore) as independent variables by controlling confounding variables including age, gender, BMI, etc. In order to determine the relationship between P1 and N2 peaks and swallow and cough function, we will fit a second multiple regression model with P1 and N2 (amplitude and gating ratio), cough and swallow outcomes as the dependent variables and disease duration as the primary independent variable by controlling confounding variables including age, gender, BMI, etc. Also, model selection technique will be adopted to select the optimal model. Besides the primary outcomes of P1 and N2 peaks, other secondary outcomes such as N1 and P2 amplitudes and gating ratios will be analyzed.

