### Preliminary Studies:

[figure not shown]

Figure 2. Significant differences (\* indicates  $p < .010$ ) between healthy controls (HC) and PD groups according to swallowing safety (PA scores; panel A) and disease severity (Hoehn & Yahr scale; panel B).

of various intensities. Our study compared 14 patients with PD to 13 age and sex matched healthy adults (HCs). The results show that people

with PD exhibit blunted magnitude estimation of inspiratory resistive loads as compared with the control group regardless of whether they exhibit measurable decline in swallowing safety, or of disease severity (Figure 2 panels A and B). These data indicate general respiratory sensation is blunted even when dysphagia is not present, and in the early stages of the disease, thus lending preliminary support to the hypothesis that blunted respiratory somatosensation precedes the onset of swallowing deficits in PD.

*Reflex cough sensitivity is blunted in later PD compared to earlier PD and age-matched controls:* In an ongoing study we are measuring sensitivity to the airway irritant capsaicin by examining the perceived UtC. To date, participants include 76 men and women with PD, ranging from 1 to 23 years post-diagnosis and 51 age-matched control participants. Our interim analysis show that participants within 10 years of diagnosis (Figure 3, PD 1-4 and PD 5-9 groups) do not exhibit a significant difference in the UtC sensitivity as compared to the control group, however the PD 10+ group does exhibit a significantly blunted UtC sensitivity compared to controls (Figure 3).

*General respiratory sensation is blunted in PD, independent of disease severity or swallowing safety:* In order to understand whether people with PD experience blunted respiratory somatosensation we conducted a preliminary study to examine the perception and magnitude estimated of inspiratory loads

[figure not shown]

Figure 3. Urge to cough (UtC) sensitivity slope comparison between healthy controls (HC), and PD duration groups. PD1-4 is 1-4 years post PD diagnosis; PD5-9 is 5-9 years post PD diagnosis; PD 10+ is more than 10 years post PD diagnosis. \* is significantly different at  $p < .001$ .

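### Aim 1's duration regression cannot show whether airway-sensation blunting is present at 0–5 years or comes before cough and swallow dysfunction

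*Combined protocol and SAP*

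**What the plan says.** Hypothesis 1 (section 5, Specific Aims) has two parts. The timing part predicts that "blunted airway somatosensation will appear earlier (years 0 – 5 post-diagnosis) in the disease process than either cough or swallowing dysfunction". The correlation part predicts that by 6–10 years "blunted respiratory somatosensation will correlate with reduced reflexive cough sensitivity and effectiveness, and decline in swallow function and safety".

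The Statistical Analysis section of Protocol 1 gives Aim 1 these analyses:

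- A multiple regression with "the slope magnitude estimation as the outcome and disease duration, age, and sex as the independent variables", together with the interactions among those predictors. It is followed by an unnamed selection step: "Model selection technique will be adopted to select the optimal parsimonial model deemed for the data".
- A subgroup comparison of the same slope between PD patients with PAS of 2 or less and PD patients with PAS above 2, adjusted for confounders. It is meant to show that the slope is reduced whatever the PAS status.
- The addition of other swallow and cough variables to the model, to look at relationships.

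Under Aims 2 and 3, a further model takes the P1 and N2 measures and the cough and swallow outcomes as dependent variables, with disease duration as the main predictor.

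Protocol 1 aims for 30 participants with PD and 30 healthy controls. The preliminary work defined blunting against controls ("Our study compared 14 patients with PD to 13 age and sex matched healthy adults (HCs") and concluded that "general respiratory sensation is blunted even when dysphagia is not present, and in the early stages of the disease".

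**The concern.** The timing claim needs two comparisons. The first is load sensation at 0–5 years against normal. The second is the size of that deficit against the cough and swallow deficits at the same stage. The plan specifies neither.

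A duration coefficient answers another question: does load sensation differ between patients with shorter and longer disease? A deficit that is fully present at diagnosis and then stable leaves nothing for that coefficient to detect. A deficit that is absent until later in the disease produces a slope. The preliminary finding, summarised as "General respiratory sensation is blunted in PD, independent of disease severity or swallowing safety", makes the stable profile a plausible one, although that study grouped patients by severity and swallowing safety rather than by duration.

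The risk is that Aim 1 reports a trend, or the lack of one, as evidence on early blunting when it is evidence of neither. The selection step could also drop duration from the final model altogether.

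**Working it through.** **1. Matching analyses to the claim.**

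| Planned analysis | Early PD vs controls? | Sensory vs cough or swallow deficit at 0–5 years? |
|---|---|---|
| Load slope on duration, age, sex | No | No |
| PAS ≤2 vs PAS >2 | No, within PD only | No |
| Cough and swallow variables added to the load-slope model | No | No, gives associations |
| Aims 2 and 3: cough and swallow outcomes on duration | No | No, no comparison across functions |

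The PAS comparison can show that load slope is similar in the two PD groups. Without a normal reference it cannot show that the slope is reduced in either.

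**2. Inputs for a simulation.** The plan gives no alpha, effect size, SD or power for Aim 1, so there is no planned figure to reproduce. From the documents: 30 PD and 30 controls; duration, age and sex as predictors. Assumed: duration D uniform on 0–15 years, residual SD 1, two-sided alpha 0.05, no interactions, no model selection.

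- PD: y = −δ(D) + e. Controls: y = e, with e ~ N(0, 1).
- Trend test: regress y on D, age and sex in the 30 PD patients, and test the coefficient of D.
- Direct contrast: two-sample t-test of PD with D ≤ 5 against the 30 controls.
- Expected early patients: 30 × 5/15 = 10.

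**3. Rejection rates.**

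| Deficit profile δ(D) | Trend | Direct contrast |
|---|---|---|
| None | 5% | 5% |
| Early: 1 SD from diagnosis, flat | 5% | 75% |
| Early: builds to 1 SD over years 0–5, then flat | 20% | 26% |
| Early: 0.5 SD at diagnosis, plus 0.1 SD/year | 57% | 50% |
| Late: 0.1 SD/year after year 5 (1 SD at year 15) | 36% | 5% |
| Late: 1 SD step at year 10 | 45% | 5% |
| Late: 1 SD step at year 5 | 46% | 5% |
| Late: 0.2 SD/year after year 5 (2 SD at year 15) | 87% | 5% |

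Check on the 75%: with 10 against 30, the standard error is √(1/10 + 1/30) = 0.365, so a 1 SD deficit gives 1/0.365 = 2.74. Normal-approximation power is Φ(2.74 − 1.96) = 0.78. The simulated value is slightly lower because of the t distribution and the varying number of early patients. Adjusting the contrast for age and sex gives about 72%.

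**4. Reading the table.** Across early profiles the trend rejects 5–57% of the time; across late profiles, 36–87%. The ranges overlap, and the flat early profile cannot be told from no deficit at all. The direct contrast stays at about 5% under every late profile.

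**5. Other readings of the model**, at deficits of 0.8 and 1.2 SD:

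- Duration in bands within PD: 5% under a flat early deficit, and 36% and 69% under onset at year 10.
- Controls included with duration set to 0: 63% and 91% under a flat early deficit, and 44% and 71% under onset at year 10. The test now has power, but it still does not separate early from late onset.
- A single PD-versus-control term is also not enough. Under the 0.2 SD/year late profile it rejects a little over 60% of the time, although nothing is present at 0–5 years.

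**The case against.** A reader might infer that the planned test is null whenever Hypothesis 1 is true and significant whenever onset is late. The documents do not support that.

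- Hypothesis 1 says when blunting appears. It does not say that blunting is complete at diagnosis and constant afterwards, and the figure with the hypothesised course is not shown. If blunting builds or worsens, the trend is non-zero even though the hypothesis holds.
- The section does not say that duration enters linearly or that the model is restricted to PD. Both are natural readings, since duration is a plain covariate and undefined for controls, but the population and functional form are unstated.
- The 87% figure needs a late deficit reaching 2 SD. Capped at 1 SD, the rate is about 36–46%, and adding the planned interactions lowers it to about 26–37%. Nor is this a type I error: the trend test's own null is false there, so it rejects correctly. The error would lie in reading the rejection as evidence of early blunting, and the plan states no such decision rule.
- The PAS comparison does bear on whether sensory loss exists without swallowing dysfunction, the Aims 2 and 3 models do relate cough and swallow to duration, and adding cough and swallow variables under Aim 1 is aimed at the correlation part.

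All of this stands and limits how strongly the point can be put. None of it supplies a control reference for early PD or a comparison across functions.

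**Conclusion.** The point holds as a mismatch between hypothesis and analysis. Followed as written, the Aim 1 analyses cannot test whether load sensation is already blunted at 0–5 years, or whether that blunting comes before cough or swallow dysfunction. This is more than missing detail: within PD, neither a linear nor a banded duration test would answer the question, and coding controls as duration 0 would not isolate early onset.

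The size depends on the assumed duration distribution, SD and effect sizes, none of which the documents give. The least assumption-dependent result is that a flat early deficit leaves a within-PD duration term rejecting at its alpha level. The late-onset and worsening figures show only that a significant trend does not discriminate between the two accounts. The correlation part of Hypothesis 1 is not affected by this point.

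**What to change.** Amend the Aim 1 text before analysis:

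1. State the analysis population and how controls enter each model.
2. Prespecify, as the Aim 1 test of early blunting, an age- and sex-adjusted contrast of load slope between PD patients at 0–5 years and controls, with a 95% CI. Exempt this contrast from model selection.
3. Report the same early-PD-versus-control contrast for the cough and swallow outcomes alongside it, with 95% CIs. Do not infer order of onset from one contrast being significant and another not.
4. Use standardised within-patient differences only for continuous measures such as UtC slope and swallow timing. Analyse PAS with an ordinal method, and C2 with a method that allows for patients who do not reach it within the 0–500 µM range. Standardising PAS against controls could fail if controls cluster at the lowest score.
5. Keep the duration trend as descriptive.

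The cost is plan wording and modest extra analysis of measures already scheduled. The drawback is precision. With about 10 early patients under the assumed distribution, the 95% CI half-width is roughly 1.96 × 0.365 = 0.72 SD, and a deficit still building over years 0–5 would often be missed (26% rejection above). The report should say so.

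### Hypothesis 1 expects load sensation to correlate with cough and swallow function by 6-10 years after diagnosis, but no planned analysis estimates that association by disease duration

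*Combined protocol and SAP*

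**What the plan says.** Section 5 (Specific Aims) states Hypothesis 1 in two clauses. The first is about order: "blunted airway somatosensation will appear earlier (years 0 – 5 post-diagnosis) in the disease process than either cough or swallowing dysfunction". The second is about association at a given stage: "by 6-10 years post-diagnosis, blunted respiratory somatosensation will correlate with reduced reflexive cough sensitivity and effectiveness, and decline in swallow function and safety".

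The Statistical Analysis section of Protocol 1 gives the Aim 1 model. The outcome is the slope of magnitude estimation for the resistive loads. The predictors are "disease duration, age, and sex as the independent variables in addition to their mutual interaction terms". Then: "Model selection technique will be adopted to select the optimal parsimonial model deemed for the data". Neither the technique nor the candidate terms are named.

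The one subgroup analysis is to "compare the slope magnitude estimation between PD patients with PAS (penetration-aspiration scale) no more than 2 and PD patients with PAS greater than 2", adjusted for age, gender, BMI and similar factors. Cough and the remaining swallow measures enter through one sentence: "We will include other swallow and cough outcome variables in this model to determine relationships between dependent variables".

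On size, Protocol 1 says "We aim to recruit 30 participants in each group", meaning 30 PD participants and 30 controls. It sets no recruitment targets by disease duration and gives no power calculation for Aims 1-3.

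**The concern.** The second clause of Hypothesis 1 concerns the link between sensation and function at a particular stage of disease. Testing it needs an estimate of that link at 6-10 years. Showing that the link emerges with time also needs a comparison with 0-5 years. In regression terms this is a duration-by-function (or duration-by-sensation) interaction, or separate estimates by duration group.

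The interactions in the Aim 1 model are among duration, age and sex. They let the load slope change with duration differently by age or sex. They do not let the link between load slope and function change with duration.

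What is at stake is interpretation. A significant pooled association would not show that it is present at 6-10 years or absent before. A null pooled association would not rule out one confined to later disease.

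**Working it through.** **Plan's own figure.** There is none for Aim 1. The only sample-size calculation in the document is for Aim 4, which does not involve the load slope.

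**Step 1: can the Aim 1 text supply a 6-10 year association?** The sentence that brings in cough and swallow measures can be read in two ways.

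- *As predictors of the load slope.* Each measure gets one coefficient, pooled over all durations.
- *As further outcomes alongside the load slope.* Each is regressed on duration, age and sex. No coefficient then links load slope to function. At most there is one residual correlation, again pooled over durations.

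If the sentence refers instead to the comparison by penetration-aspiration score, that comparison is also pooled over duration. No reading gives a 6-10 year association.

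**Step 2: does another aim supply it?**

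- Aims 2 and 3: the second model has evoked-potential, cough and swallow measures as dependent variables and duration as the main predictor. The load slope is absent.
- Aim 4: Protocol 2 carries over pulmonary function, depression and apathy, cough and swallowing procedures. The resistive loads are not among them.

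**Step 3: what does the pooled coefficient estimate?** Take standardised variables with equal variance in each duration group. The pooled coefficient is then about the weighted mean of the group associations.

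- 15 participants at 0-5 years with correlation 0 and 15 at 6-10 years with 0.6: (15 × 0 + 15 × 0.6)/30 = 0.30.
- Constant correlation 0.3: 0.30.
- 10 each at 0-5, 6-10 and beyond 10 years with 0, 0.6 and 0.6: (0 + 0.6 + 0.6)/3 = 0.40, the same as a constant 0.4.

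The ambiguity therefore does not depend on the 15/15 split.

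Simulation check: 3000 runs, 30 PD participants split 15/15, ordinary least squares, two-sided 0.05. The load slope was regressed on linear duration, age, sex, their two-way interactions and one function measure. The last column adds function × duration.

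| True correlation, early / late | Mean pooled coefficient | Pooled coefficient significant | Interaction significant |
|---|---|---|---|
| 0 / 0.5 | 0.25 | 24% | 17% |
| 0 / 0.6 | 0.30 | 31% | 27% |
| 0 / 0.7 | 0.35 | 40% | 35% |
| 0.3 / 0.3 | 0.30 | 30% | 5% |

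Rows two and four are indistinguishable on the planned coefficient. Only the interaction separates them, and with low power.

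**Step 4: how much can 30 PD participants show?** In regression simulations for late correlations of 0.5, 0.6 and 0.7, the interaction test is significant in:

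- 23%, 34% and 45% of runs with a 15/15 split and grouped duration;
- 15%, 20% and 29% with 10 each at 0-5, 6-10 and 10-23 years and linear duration.

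A Fisher-z comparison of two correlations, 0 against r, has power Φ(atanh(r)/SE − 1.96), with SE = √(1/(n₁−3) + 1/(n₂−3)).

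- 10 per group: SE = √(2/7) = 0.535. For r = 0.6, 0.693/0.535 − 1.96 = −0.66, giving 25%. For 0.5 and 0.7 it gives 18% and 37%.
- 15 per group: SE = √(2/12) = 0.408. It gives 27%, 40% and 57%. This approximation has no covariates and runs above the regression figures.

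For 80% power against 0 early, the late correlation would have to be about 0.82 (15 per group) or 0.90 (10 per group).

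Interval width for an observed correlation of 0.6 is tanh(0.693 ± 1.96/√(n−3)): 0.13 to 0.85 with 15 participants, −0.05 to 0.89 with 10.

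**The case against.** **Aim 1 is broader than the clause.** It asks for relationships between sensation, cough and swallowing without a duration condition, and a pooled association answers that. The duration term also addresses how load sensation itself changes with duration. Both points stand. They confine the gap to the second clause of Hypothesis 1 and lower its severity.

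**Model selection could bring in the interaction.** The text does not forbid it. But the technique and candidates are unnamed, and a term that may or may not be selected is not a prespecified test.

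**The sample is too small for an interaction test.** This is true on every setting tried. It argues for estimates with intervals, not for a pooled coefficient that answers a different question.

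A reader might also infer four stronger things that the documents do not support.

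- *That the plan puts cause and effect on the wrong sides.* This treats one reading of an ambiguous sentence as settled. The same words fit cough and swallow measures entering as further outcomes, as Aims 2 and 3 state explicitly.
- *That the pooled coefficient loses power and a duration-specific one gains it.* With a 15/15 split and grouped duration, the pooled coefficient is significant in 26%, 35% and 46% of runs and the late association in 43%, 61% and 77%. With 10 each at 0-5, 6-10 and 10-23 years, the association persisting and duration linear, this reverses: 42%, 57% and 71% pooled against 37%, 51% and 66% at 8 years. Grouping everyone beyond 5 years turns it again, to 59%, 78% and 91% for the late group. The eligibility criteria set no upper limit on duration, so the documents do not settle which mix applies.
- *That the hypothesis says correlation is zero, or function intact, at 0-5 years.* It says blunting appears earlier than dysfunction. Zero is a working assumption here.
- *That Aim 1 as a whole cannot be answered.* It can, as an overall association.

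**Conclusion.** The concern holds in a limited form. The Aim 1 analysis plans no duration-specific estimate of the association between load sensation and cough or swallow function, and no other aim supplies one. The result would look the same whether the association emerges by 6-10 years or is constant: about 0.30 in both cases under the assumed 15/15 split with 0 early and 0.6 late.

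The gap itself follows from the text and needs no assumption. The figures rest on assumed correlations, an assumed duration mix, a zero early correlation and two-sided 0.05, none of which the plan gives for Aim 1.

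This should be fixed, but it is not critical. It affects one clause of one hypothesis, and with 30 PD participants even the right model will describe the change rather than establish it.

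**What to change.** Amend the Aim 1 analysis, in PD participants only, as follows.

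1. For each named cough and swallow outcome, fit the outcome on load slope, duration group (0-5, 6-10, more than 10 years), load slope × duration group, age and sex. State how durations between 5 and 6 years are assigned, for example by completed years.
2. Name one lead cough outcome and one lead swallow outcome; label the rest supportive. The penetration-aspiration score is already the plan's primary swallowing outcome and should be analysed as ordinal.
3. Keep the load-slope and interaction terms out of model selection.
4. Report the association with its 95% interval in each duration group, and the contrast between 0-5 and 6-10 years, as estimation rather than a powered test.
5. State that the interaction test has roughly 15-50% power for late correlations of 0.5-0.7, depending on duration mix and coding. Claim no gain in power.
6. Reword the sentence on adding swallow and cough variables so that each variable's role is explicit.

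**Cost.** No new data or visits. Intervals within each duration group will be wider than a pooled one. With three duration groups the interaction adds two parameters per model. There is one model per outcome: counting airflow measures once, the Protocol 2 list has six cough measures (urge-to-cough slope, C2, CPD, PEFR, PEFRT, CVA) and six swallow measures (PAS, SRT, dtLVC_H1, dtLVC_B1, dLVC, PTT), so twelve. That number is the reason for naming lead outcomes.
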